5.2 Interim Analyses

No formal interim analysis is planned for this study.

5.3 Population PK Analysis

Population PK analysis will be described in a separate Pharmacokinetic Analysis Plan.

5.4 Analyses and Reporting

All final, planned analyses identified in the protocol and in this SAP will be performed after the last patient completes the Core Phase and after the last patient completes the Extension Phase.

6 Sample Size Determination

To determine a clinically relevant efficacy hurdle, data from a 26-week open-label extension of eltrombopag study TRA108109 in adult Japanese patients with chronic ITP were used as a benchmark. This study evaluated the endpoint of cumulative number of weeks of platelet response ($\geq 50 \times 10^9/L$) in a comparable population of patients who received eltrombopag for 26 weeks. The results were similar to those in avatrombopag overseas Study 302, with a reported mean of 11.2 weeks with 95% CI of 8.02 and 14.38 weeks.

The lower limit of the 95% CI of the cumulative number of weeks of platelet response, or 8.02, from study TRA108109 is set as the efficacy hurdle for the lower limit of the 95% CI in this study. Assuming a distribution of results (mean of 12.0 cumulative weeks and standard deviation of 8.75) similar to that observed in Study 302, a sample size of 19 subjects would be required to meet this primary efficacy endpoint hurdle.

7 Analysis Populations

7.1 Consented Population

The Consented Population will include all subjects who gave informed consent.

7.2 Full Analysis Set (FAS)

The Core Phase FAS will include all subjects who are enrolled into the study and gave informed consent.

The Extension Phase FAS will include all subjects who enter the Extension Phase.

7.3 Per Protocol Set (PPS)

The Core Phase PPS will include all enrolled subjects who receive protocol-assigned study drug and who do not meet any pre-specified criteria. A comprehensive list of criteria for exclusion from the PPS will be agreed upon by the study team and documented prior to database lock.

Examples of these criteria may include:

- Use of certain prohibited concomitant medications
- Selected Inclusion/Exclusion criteria not met for the Core Phase
- Lack of compliance with study medication during the Core Phase

7.4 Safety Set (SAF)

The Core Phase Safety Set will include all subjects who receive at least 1 dose of study drug and have a post-dose safety assessment. The Extension Phase Safety Set will include all subjects who receive at least 1 dose of study drug in the Extension Phase and have a post-dose safety assessment in the Extension Phase. General Issues for Statistical Analysis.

8 General Issues for Statistical Analysis

8.1 Statistical Analysis and Tabulation Software

Below are the software and its versions used in this study.

| | Software/Version |
|-------------------------------|--|
| Operating system | Microsoft Windows Server 2016 Standard |
| Statistical analysis software | SAS 9.4 or later |
| Tabulation Software | Microsoft Word 2016 or later. |

8.2 Dictionaries

Below are the dictionaries used in this study.

| Category | Dictionary | Remarks |
|--|--|--|
| Adverse Events | MedDRA Version.26.1 or later | System organ class (SOC) and preferred term (PT) will be determined for each adverse event and these will be used in analyses. |
| Medical Histories | MedDRA Version.26.1 or later | The same as adverse events. |
| Name of Medication (Prior and Concomitant Medications) | WHO Drug Global September 1, 2023 or later | Anatomical Therapeutic Chemical (ATC) level 2 Preferred Name |

8.3 Analysis Methods

8.3.1 Descriptive Statistics

Descriptive statistics:

| | |
|--------------------------------|--|
| Continuous data except for PK | PK concentration data |
| The number of subjects (N) | The number of subjects (N) |
| Arithmetic Mean | Arithmetic Mean |
| Standard Deviation (SD) | Standard Deviation (SD) |
| Median | Median |
| Minimum and Maximum | Minimum and Maximum |
| First quartile, Third quartile | - |
| - | The number and % of BLQ |
| | Coefficient of variation (CV%) for arithmetic mean |
| - | Geometric Mean |
| - | 95% confidence interval (CI) of geometric mean |
| - | Geometric CV% |

CV%, Geometric mean, 95% CI of geometric mean, and Geometric CV% are calculated using the following formula:

CV(%) = (standard deviation) / (arithmetic mean) × 100

$$\text{Geometric mean} = \exp \left[\frac{\sum_{i=1}^n \log X_i}{n} \right] = \sqrt[n]{\prod_{i=1}^n X_i}$$

95% CI of geometric mean = $\exp(\mu \pm 1.96 \cdot s/\sqrt{n})$

μ : mean on the natural logarithm scale

s: standard error on the natural logarithm scale

$$\text{Geometric CV(%) = } \sqrt{\exp(s^2) - 1} \times 100$$

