### 4 STUDY DESCRIPTION

# 4.1 Summary of Study Design

This study is an open-label study of avatrombopag in Japanese men and women  $\ge 18$  years who have chronic ITP. Approximately 19 subjects who meet all the eligibility requirements will be enrolled. The Screening Visit and Day 1 Baseline Visit platelet counts will be averaged to obtain the baseline platelet count value. The 2 samples must be obtained  $\ge 48$  hours and  $\le 2$  weeks apart and the results must be available prior to enrollment. No single platelet count can be  $> 35 \times 10^9 / L$ . An additional screening platelet count is required if the second platelet count is outside of the 2-week window.

Subjects will receive a starting dose of 20 mg avatrombopag once daily and will be allowed to change their dose and dosing frequency (maximum dose 40 mg daily, minimum dose 20 mg once weekly) in accordance with their individual platelet responses. The overall goal of any dose modification will be to maintain the platelet count  $\geq 50 \times 10^9/L$  and  $< 200 \times 10^9/L$ , and to decrease the need for concomitant ITP medications.

The study will consist of 3 phases: Pre-enrollment, Primary Investigation (Core Phase), and Extension. The Pre-enrollment Phase will have 1 Screening Period (up to 4 weeks). The Primary Investigation Phase (Core Phase) will have 4 periods: Baseline (1 day), Titration (6 weeks), Concomitant ITP Medication Reduction (12 weeks), and Maintenance (8 weeks including the Endof-Treatment [EOT] Visit). Subjects will have weekly or bi-weekly visits during the 26-week Primary Investigation Phase (Core Phase) to collect the required platelet count data, bleeding events, and other AEs. All subjects who complete the Primary Investigation Phase (Core Phase) can continue to receive avatrombopag in the Extension Phase until market authorization in Japan. Safety and efficacy data will be collected monthly in the Extension Phase. Dose-tapering and Follow-up at the end of the Core Phase are required only for those subjects not continuing into the Extension Phase.

The total study duration of the Pre-enrollment and Primary Investigation Phase will be up to 7 months. Subjects may continue in the Extension Phase until market authorization in Japan.

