4.2 Selection of Study Population

This study will enroll at least 19 Japanese adults with chronic ITP (≥ 12 months duration) and an average of 2 platelet counts $< 30 \times 10^9 / \text{L}$, who meet all eligibility criteria.

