| Visit 8 (Week 6) | Sparse | During clinic visit |
| Visit 10 (Week 10) | Serial | 
 • Pre-dose • Between 2 and 4 hours post-dose • Between 6 and 8 hours post-dose |
| Visit 13 (Week 16) | Sparse | During clinic visit |
| Visit 22 (Week 26) | Sparse | During clinic visit |

The data handling methods for Pharmacokinetic Concentrations are presented below:

1) Data Handling for Below the Lower Limit of Quantification (BLQ)

If the recorded plasma avatrombopag concentration is below the limit of quantification (BLQ), the measured value of the concentration will be treated as the following:

- For tables, BLQ will be substituted by 0.
- For listings, display BLQ as “BLQ”.

2) Data Handling for Missing Value

If missing data is recorded for plasma avatrombopag concentration, imputation of the records will not be performed. Thus, any missing records for plasma avatrombopag concentration will be excluded from analysis.

If blood concentration is not measured (not done) then it is considered as missing.

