12.1 Summary of Avatrombopag Concentrations

Population: Full Analysis Set

Target Phases: Core Phase

Analysis items: - Avatrombopag concentrations in plasma

Visits: - Visit 5 (Week 2), Visit 10 (Week 10): Pre-dose, Between 2 and 4 hours postdose, Between 6 and 8 hours postdose.
- Visit 4 (Day 8), Visit 7 (Week 4), Visit 8 (Week 6), Visit 13 (Week 16), Visit 22 (Week 26).

Contents: - Calculate the descriptive statistics of avatrombopag concentrations in plasma by analysis visits/time points.

Definitions: - Regarding summary statistics of avatrombopag concentrations, refer to [8.3.1 Descriptive Statistics](#).

13 Safety Analyses

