Appendix 1: Sample Code

- Confidence Intervals for proportions

```
proc freq data=data;  
  tables targvar /out=cnt binomial alpha=0.05;  
  exact binomial;  
  ods output binomial= binomial;  
run;
```

Exact CI should be used.

- Confidence Intervals for mean

```
proc ttest data=data alpha=0.05;  
  class param;  
  var Height;  
run;
```

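### SAP 8.3.1 uses the normal multiplier 1.96 for the 95% CI of the geometric mean concentration, so with about 19 subjects the descriptive PK intervals are slightly too narrow

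*SAP*

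**What the plan says.** SAP 8.3.1 lists one set of summary statistics for PK concentrations and another for all other continuous data. Only the PK set contains the "95% confidence interval (CI) of geometric mean". The formula given is "95% CI of geometric mean = $\exp(\mu \pm 1.96 \cdot s/\sqrt{n" (closing brackets follow), and the legend reads "s: standard error on the natural logarithm scale".

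SAP 12.1 applies these statistics in the Core Phase: "Calculate the descriptive statistics of avatrombopag concentrations in plasma by analysis visits/time points". That is 11 time points: two serial visits with three samples each, plus five sparse visits.

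On the number of values, Protocol 4.1 says "Approximately 19 subjects who meet all the eligibility requirements will be enrolled", while SAP 4.2 says "This study will enroll at least 19 Japanese adults with chronic ITP". SAP section 12 adds that "any missing records for plasma avatrombopag concentration will be excluded from analysis", and Protocol 5.3 states that subjects who terminate early are not replaced. SAP section 12 also sets values below the limit of quantification (BLQ) to 0 in tables.

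For intervals of ordinary means, the sample code in SAP Appendix 1 is "proc ttest data=data alpha=0.05", a procedure that returns a t interval. Neither document gives a t-based version for the geometric mean.

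**The concern.** The value 1.96 gives 95% coverage only when the standard deviation is known. Here it is estimated on the log scale from the same small set of values as the mean. The multiplier should then be the t quantile with n−1 degrees of freedom, which is larger at every n this study can reach. An interval labelled 95% will therefore cover less than 95%, and the gap widens as n falls.

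What is at stake is the stated precision of a descriptive exposure table. Collecting PK data in Japanese subjects is an exploratory objective (Protocol 2.1.3, SAP 3.1.3), and population PK modelling has its own plan (SAP 5.3). The table in SAP 12.1 is therefore the PK summary that this SAP controls directly.

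**Working it through.** **Inputs.** Multiplier 1.96, s and n as in SAP 8.3.1; planned n about 19 (Protocol 4.1) or at least 19 (SAP 4.2). The documents give no expected number of concentrations per time point and no dropout rate, so every other n below is an assumption.

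**The plan's figure.** The two-sided 95% standard normal quantile is 1.95996, so 1.96 is the large-sample value with no small-sample adjustment.

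**Which s.** The legend calls s a standard error, yet the formula divides it by √n again. SAP 8.3.1 also puts s into the geometric CV, √(exp(s²) − 1), where a standard deviation belongs. With a true geometric CV of 60% and n = 19, entering the standard error there would print about 13%. The main calculation therefore reads s as the log-scale standard deviation.

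**Coverage and width.** For normally distributed log-concentrations:

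- coverage of the 1.96 interval = 2·F(1.96) − 1, with F the t distribution function on n−1 degrees of freedom;
- required increase in log-scale width = t(0.975, n−1)/1.96 − 1.

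| n | t(0.975, n−1) | Width should be larger by | Coverage with 1.96 |
|---|---|---|---|
| 10 (assumed) | 2.262 | 2.262/1.96 − 1 = 15.4% | 91.8% |
| 15 (assumed) | 2.145 | 2.145/1.96 − 1 = 9.4% | 93.0% |
| 19 (planned) | 2.101 | 2.101/1.96 − 1 = 7.2% | 93.4% |
| 25 (assumed) | 2.064 | 2.064/1.96 − 1 = 5.3% | 93.8% |

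A simulation of 400,000 samples of size 19 gave 93.5%, in agreement.

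**On the concentration scale.** The documents give no geometric CV, so take 60% as an assumption, with a range of 40% to 80%. The log-scale standard deviation at 60% is √(ln(1 + 0.6²)) = 0.5545. At n = 19 the half-width is 1.96 × 0.5545/√19 = 0.249, against 2.101 × 0.5545/√19 = 0.267. Limits as multiples of the geometric mean:

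| Geometric CV (assumed) | With 1.96 | With t |
|---|---|---|
| 40% | 0.841 to 1.189 | 0.831 to 1.204 |
| 60% | 0.779 to 1.283 | 0.765 to 1.306 |
| 80% | 0.729 to 1.372 | 0.712 to 1.404 |

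**If s is taken literally as the standard error.** The effective multiplier at n = 19 becomes 1.96/√19 = 0.450, and coverage is about 34%. With t it becomes 2.101/√19 = 0.482, and coverage is about 36%. Changing the multiplier alone would therefore not give a 95% interval under the legend as printed.

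**Where no interval exists.** If any value at a time point is BLQ and set to 0, its logarithm is undefined and the product form of the geometric mean is 0. The formula returns no interval there, whatever the multiplier.

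**The case against.** The strongest reply is that this is a small refinement to exploratory, descriptive output. At the planned size it costs 1.6 points of coverage (95 − 93.4), no testing is planned unless noted (SAP 8.3.5), and the unclear meaning of s in the same formula matters far more. That is fair as to size and priority. It is not a reason to keep 1.96: with s properly defined, the interval would still be too narrow.

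A second reply is that a t interval is itself exact only for log-normal data. The by-visit summaries pool individually titrated regimens (Protocol Table 1), and sparse samples are timed only as during the clinic visit. This stands: 95% is not guaranteed after the change. It does not favour 1.96, which rests on the same assumption and also treats the standard deviation as known.

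A reader might go further on four points that the documents do not support:

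- **A contradiction with Appendix 1.** That code is a template for ordinary means, and SAP 8.3.1 has its own explicit formula for the geometric mean. Appendix 1 shows that the SAP uses t intervals elsewhere; it does not govern this one.
- **Every PK interval is affected.** Time points with a BLQ value set to 0 have no interval to correct.
- **n will fall well below 19.** Smaller n is possible, but nothing predicts it, and SAP 4.2 allows more than 19.
- **The intervals will be set against overseas PK data.** Protocol 1.5 and SAP 4.1 speak generally of comparing this study with Study 302. Neither names these intervals.

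**Conclusion.** The point holds, as a minor one. At n = 19, with s as the log-scale standard deviation and log-normal concentrations, the interval labelled 95% covers 93.4% and its log-scale width should be 7.2% larger. The direction is the same at any n the study could reach.

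It would be wrong to infer that the efficacy conclusion is at risk. The primary endpoint uses the confidence interval of an arithmetic mean, to which this formula does not apply. It would also be wrong to infer that exchanging the multiplier is enough by itself; that works only once s is defined as a standard deviation.

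**What to change.** In SAP 8.3.1, replace 1.96 by t(0.975, n−1), with n the number of concentrations summarised at that time point. In the same edit, define s as the standard deviation on the natural-log scale, which also makes the geometric CV formula consistent.

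This needs no new data and leaves the efficacy analyses unchanged. The downside is intervals slightly wider than those from 1.96 with s as the standard deviation: 7.2% on the log scale at n = 19.

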# 10.2.3 Analysis of Safety

Evaluation of safety will be performed on the Safety Set. Safety data that will be evaluated include AEs, clinical laboratory results, and vital signs. All AEs will be coded using MedDRA. Adverse events will be coded to system organ class and preferred term using MedDRA. AEs will be presented with and without regard to causality based on the Investigator's judgment. The frequency of overall toxicity, categorized CTCAE criteria Grades 1 through 5, will be described. Treatment-emergent AEs (TEAEs) will be summarized by presenting the incidence of AEs. Descriptive summary statistics (mean plus standard deviation, median, and range) of the laboratory parameters, vital signs, and changes from baseline will be evaluated.

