5.1 Changes from Planned Analyses in the Protocol

A secondary efficacy endpoint was included which was not detailed in the protocol: Proportion of subjects with a reduction in use of concomitant ITP medications from baseline.

Bleeding Adverse Events of Special Interest (AESIs) were first identified using a Standardised Medical Dictionary for Regulatory Activities Query (MedDRA SMQ) and then further defined as clinically significant using reported Common Terminology Criteria for Adverse Events (CTCAE) grade for the event rather than the WHO bleeding grade, as WHO bleeding grades collected at study visits are not linked to specific adverse events.

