8.3.3 Change from Baseline

Change from baseline at each time point is defined by the following formula:

$$\text{Change from baseline} = \frac{\text{Value at each time point}}{\text{Baseline value}} - 1$$

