8.4 Rounding Digits

8.4.1 Displaying of Descriptive Statistics

- 1) Parameters except for avatrombopag concentration
 - Mean, median, first quartile, third quartile and 95% CI for mean will be displayed in one digit lower than the display digit.
 - Standard deviation will be displayed in two digits lower than the display digit.
 - Minimum and maximum will be displayed in display digit.
- 2) Avatrombopag concentration

Minimum, maximum, mean, standard deviation, median, geometric mean and 95% CI of geometric mean will be rounded and then displayed as 3 significant digits.

The example of rounding and displaying as 3 significant digits:

| Value | Displayed as 3 significant digits |
|----------|-----------------------------------|
| 1234.5 | → 1230 |
| 1.2345 | → 1.23 |
| 243467 | → 243000 |
| 243667 | → 244000 |
| 0.057226 | → 0.0572 |
| 0.057276 | → 0.0573 |

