11.3.3 Platelet Count ($10^9/L$) and Change from Baseline by Visit

| | |
|-----------------|---|
| Population: | Full Analysis Set, Per Protocol Set (for Core Phase only) |
| Target Phases: | Core Phase, Extension Phase |
| Visits: | 
- Core Phase: Baseline - Visit 22 (Week 26)- Extension Phase: E 1 (Month 1) - Last Visit |
| Analysis items: | 
- Measured value and change from baseline for platelet count |
| Contents: | 
- Summary statistics of platelet count from local laboratories for all subjects in each visit are calculated. |

11.3.4 Median (Q1, Q3) Platelet Count ($10^9/L$) of Local Platelet Count Over Treatment Period

| | |
|-----------------|--|
| Population: | Full Analysis Set, Per Protocol Set (for Core Phase only) |
| Target Phases: | Core Phase, Extension Phase |
| Visits: | 
- Core Phase: Baseline - Visit 22 (Week 26)- Extension Phase: E 1 (Month 1) - Last Visit |
| Analysis items: | 
- Median, Q1, and Q3 values of measured values and change from baseline values |
| Contents: | 
- Series plot for median (Q1, Q3) platelet count from local laboratories will be presented graphically by visit. |

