13.3.1 Laboratory Parameters and Change from Baseline by Visit

Population: Safety Set

Target Phases: Core Phase, Extension Phase

Visits:

- Core Phase: Baseline, Visit 4 (Day 8), Visit 10 (Week 10), Visit 13 (Week 16), Visit 22 (Week 26), Follow-up (Week 1), Follow-up (Week 2), Follow-up (Week 3), Follow-up (Week 4)
- Extension Phase: E 1 (Month 1), E 2 (Month 2), E 4 (Month 4), E 5 (Month 5), E 7 (Month 7), E 8 (Month 8), E 10 (Month 10), E 11 (Month 11), E 13 (Month 13), E 14 (Month 14), E 16 (Month 16), E 17 (Month 17), E 19 (Month 19), E 20 (Month 20), E 22 (Month 22), E 23 (Month 23), E 24 (Month 24)

Analysis items:

- For the parameters to be analyzed refer to Table 1 in [13.3 Laboratory data](#)

Contents:

- Summary statistics of actual value and change from baseline of laboratory tests for each visit are calculated.

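### SAP 8.3.1 labels s as the log-scale standard error in two formulas that need the log-scale SD, and SAP 8.3.3 defines change from baseline as an unlabelled ratio minus 1

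*SAP*

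**What the plan says.** **Geometric statistics.** For PK concentrations, SAP 8.3.1 gives the 95% CI of the geometric mean as exp(mu ± 1.96·s/√n) and the geometric CV as √(exp(s²) − 1) × 100. The legend reads "s: standard error on the natural logarithm scale". No other section redefines s. Appendix 1 has sample code for proportions and for an arithmetic mean, but none for geometric statistics. SAP 12.1 refers the concentration table back to 8.3.1. SAP section 12 sets values below the quantification limit (BLQ) to 0 in tables.

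**Change from baseline.** SAP 8.3.3 divides each value by the baseline value and subtracts 1. The term is then used in:
- SAP 11.3.3, "Measured value and change from baseline for platelet count", under a heading in 10^9/L;
- SAP 13.3.1, "Summary statistics of actual value and change from baseline of laboratory tests for each visit are calculated";
- SAP 13.4.1, in the same way for vital signs.

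Protocol 10.2.3 promises "Descriptive summary statistics (mean plus standard deviation, median, and range) of the laboratory parameters, vital signs, and changes from baseline will be evaluated". SAP 5.1 lists departures from the protocol's analyses. It declares an added endpoint ("A secondary efficacy endpoint was included which was not detailed in the protocol") and a new way of identifying bleeding events of special interest, and says nothing of relative change.

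**Display digits.** SAP 8.4.1 states "Mean, median, first quartile, third quartile and 95% CI for mean will be displayed in one digit lower than the display digit" and "Minimum and maximum will be displayed in display digit". The display digits in 13.3 and 13.4 belong to the raw units.

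**The concern.** For log-normal data the standard error is already SD/√n. If s is the standard error, the printed interval divides by √n twice. The geometric CV also becomes a quantity that shrinks as n grows, so it no longer measures between-subject variability.

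Change from baseline without qualification is normally read as a difference in the original unit. A ratio minus 1 has no unit, and in a table headed 10^9/L a value of 3.0 invites the reading 3 × 10^9/L when it means a fourfold count. The ratio is also undefined at a baseline of 0, which can occur for differential white-cell fractions recorded to 0.001 (SAP 13.3).

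At stake are the geometric columns of the table in 12.1 and the change columns for platelets, laboratory tests and vital signs.

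**Working it through.** The plan states no numerical result on this point, so there is none to reproduce. The check evaluates the formulas as labelled and as they need to be.

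**Inputs.** n = 19 is the planned minimum enrolment (SAP 4.2) and assumes complete samples at a time point. The 1.96 is from SAP 8.3.1. The documents give no log-scale SD of concentration; I assume 0.6, with a range of 0.4 to 1.0.

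**1. Interval for the geometric mean**
- s as SD: log half-width 1.96·SD/√n.
- s as SE = SD/√n, as labelled: log half-width 1.96·SD/n.
- Ratio: √19 = 4.36, whatever the SD.
- Coverage as labelled: 2Φ(1.96/4.359) − 1 = 34.7%; with the t distribution on 18 df, 34.2%.
- At log-SD 0.6, as multiples of the geometric mean: exp(±1.96 × 0.6/√19) = 0.76 to 1.31; as labelled, exp(±1.96 × 0.6/19) = 0.94 to 1.06.
- If s is the SD, only 1.96 against t(18) = 2.101 remains: a factor of 1.07, coverage 93.4%.

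**2. Geometric CV at n = 19**

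| Assumed log-SD | √(exp(SD²) − 1) | As labelled, √(exp(SD²/19) − 1) |
|---|---|---|
| 0.4 | 41.7% | 9.2% |
| 0.6 | 65.8% | 13.8% |
| 1.0 | 131.1% | 23.2% |

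With log-SD fixed at 0.6, the labelled version prints 27.3% at n = 5, 19.1% at n = 10 and 13.8% at n = 19: the same variability, three different answers.

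**3. Change from baseline**
- Platelets, assumed baselines 5, 15 and 25, all rising to 60. Ratios minus 1: 60/5 − 1 = 11, 60/15 − 1 = 3, 60/25 − 1 = 1.4, giving mean 15.4/3 = 5.1 and median 3.0. Differences: 55, 45, 35, giving mean and median 45 × 10^9/L. The lowest baseline supplies 11/15.4 = 71% of the ratio mean.
- Systolic pressure, assumed baseline 120 mmHg, display digit 1 (SAP 13.4). If the raw-unit digits are applied to the change column, means and medians print to 0.1, so a change below 0.05 × 120 = 6 mmHg prints as 0.0. Minima and maxima print to whole numbers, so a change below 0.5 × 120 = 60 mmHg prints as 0.

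**4. BLQ values.** SAP 8.3.1 equates exp(mean of log X) with the nth root of the product. One value set to 0 makes the first undefined and the second 0.

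**The case against.** The first point can be called a one-word slip. Both formulas are the textbook log-SD versions, the explicit division by √n shows what was meant, and standard software would probably return the SD-based values. A false geometric CV would also sit beside a much larger arithmetic CV and might be noticed. This is fair, and the 34–35% coverage is the result of literal programming, not a forecast. But 8.3.1 is the only specification of these statistics: a programmer who follows it prints wrong columns, and one who does not departs from the SAP.

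On the second point, the protocol never defines change as a difference, so a relative change does not strictly contradict it. The formula can be programmed, actual values are summarised alongside, and no listed efficacy endpoint uses platelet change from baseline. All of that stands. It does not supply the missing label, digits or zero-baseline rule. A misprinted subtraction is conceivable, but the explicit minus 1 makes it unlikely; the signed page should be checked.

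The rounding figures are conditional on how 8.4.1 is applied. The choice of t over 1.96 is a preference. The frequency of BLQ values is unknown. None of these three carries the conclusion.

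**Conclusion.** The concern holds on both counts and should be fixed. The 4.36-fold narrowing and 34–35% coverage depend only on n = 19 and literal use of the legend. The geometric CV figures (9–23% printed where 42–131% is right) also rest on an assumed log-SD of 0.4 to 1.0. The change-from-baseline definition needs no slip by a programmer to cause harm, since it would be implemented as printed; its numerical examples use assumed baselines.

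The effect is confined to descriptive tables. The primary endpoint and its 8.02-week hurdle, the Day 8 response rate, the sample size, actual-value summaries and abnormal counts do not use these formulas. Population PK has its own plan (SAP 5.3). The trial's conclusion is not threatened.

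**What to change.** - **8.3.1:** define s as the standard deviation on the natural-log scale. The two formulas then stand. Preferably replace 1.96 by the t quantile on n − 1 df.
- **8.3.3:** define change from baseline as the value at the time point minus the baseline value. If a relative change is also wanted, report it separately as percent change (× 100), with its own display digits and a rule for a baseline of 0, and record it in 5.1.
- **Section 12:** compute geometric statistics on quantifiable values only, beside the BLQ count and percentage already planned, or omit them where any value is BLQ. The first option leaves arithmetic and geometric columns with different n, which the table should show.

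The cost is SAP wording and a few lines of code before Core Phase database lock, with no new data and no change to a decision rule. Geometric-mean intervals will be wider than those from a literal reading.
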